8.2.4. Hospitalization

Hospitalization is defined as any initial admission (even less than 24 hours) in a hospital or equivalent healthcare facility, or any prolongation of an existing admission. Admission also includes transfer within the hospital to an acute/intensive care unit (eg, from the psychiatric wing to a medical floor, medical floor to a coronary care unit, or neurological floor to a tuberculosis unit). An emergency room visit does not necessarily constitute a hospitalization; however, the event leading to the emergency room visit is assessed for medical importance.

Hospitalization does not include the following:

- Rehabilitation facilities;
- Hospice facilities;
- Respite care (eg, caregiver relief);
- Skilled nursing facilities;
- Nursing homes;

- Same-day surgeries (as outpatient/same-day/ambulatory procedures).

Hospitalization or prolongation of hospitalization in the absence of a precipitating clinical AE is not in itself an SAE. Examples include:

- Admission for treatment of a preexisting condition not associated with the development of a new AE or with a worsening of the preexisting condition (eg, for workup of a persistent pretreatment laboratory abnormality);
- Social admission (eg, subject has no place to sleep);
- Administrative admission (eg, for yearly physical examination);
- Protocol-specified admission during a study (eg, for a procedure required by the study protocol);
- Optional admission not associated with a precipitating clinical AE (eg, for elective cosmetic surgery);
- Hospitalization for observation without a medical AE;
- Preplanned treatments or surgical procedures. These should be noted in the baseline documentation for the entire protocol and/or for the individual subject.

Diagnostic and therapeutic noninvasive and invasive procedures, such as surgery, should not be reported as SAEs. However, the medical condition for which the procedure was performed should be reported if it meets the definition of an SAE. For example, an acute appendicitis that begins during the reporting period should be reported if the SAE requirements are met, and the resulting appendectomy should be recorded as treatment of the AE.

8.3. Severity Assessment

GRADE	If required on the AE page of the CRF, the investigator will use the adjectives MILD, MODERATE, or SEVERE to describe the maximum intensity of the AE. For purposes of consistency, these intensity grades are defined as follows:	
1	MILD	Does not interfere with subject's usual function.
2	MODERATE	Interferes to some extent with subject's usual function.
3	SEVERE	Interferes significantly with subject's usual function.

Note the distinction between the severity and the seriousness of an AE. A severe event is not necessarily an SAE. For example, a headache may be severe (interferes significantly with the subject's usual function) but would not be classified as serious unless it met one of the criteria for SAEs, listed above.

8.4. Special Situations

8.4.1. Protocol-Specified Serious Adverse Events

There are no protocol-specified SAEs in this study. All SAEs will be reported to Pfizer Safety by the investigator as described in previous sections, and will be handled as SAEs in the safety database.

8.4.2. Potential Cases of Drug-Induced Liver Injury

Humans exposed to a drug who show no sign of liver injury (as determined by elevations in transaminases) are termed “tolerators,” while those who show transient liver injury but adapt are termed “adaptors.” In some subjects, transaminase elevations are a harbinger of a more serious potential outcome. These subjects fail to adapt and therefore are “susceptible” to progressive and serious liver injury, commonly referred to as drug-induced liver injury (DILI). Subjects who experience a transaminase elevation above 3 times the upper limit of normal (\times ULN) should be monitored more frequently to determine if they are an “adaptor” or are “susceptible.”

Liver function tests (LFTs) are not required as a routine safety monitoring procedure in this study. However, should an investigator deem it necessary to assess LFTs because a subject presents with clinical signs/symptoms, such LFT results should be managed and followed as described below.

In the majority of DILI cases, elevations in aspartate aminotransferase (AST) and/or alanine aminotransferase (ALT) precede total bilirubin (TBili) elevations ($>2 \times$ ULN) by several days or weeks. The increase in TBili typically occurs while AST/ALT is/are still elevated above $3 \times$ ULN (ie, AST/ALT and TBili values will be elevated within the same laboratory sample). In rare instances, by the time TBili elevations are detected, AST/ALT values might have decreased. This occurrence is still regarded as a potential DILI. Therefore, abnormal elevations in either AST OR ALT in addition to TBili that meet the criteria outlined below are considered potential DILI (assessed per Hy’s law criteria) cases and should always be considered important medical events, even before all other possible causes of liver injury have been excluded.

The threshold of laboratory abnormalities for a potential DILI case depends on the subject’s individual baseline values and underlying conditions. Subjects who present with the following laboratory abnormalities should be evaluated further as potential DILI (Hy’s law) cases to definitively determine the etiology of the abnormal laboratory values:

- Subjects with AST/ALT and TBili baseline values within the normal range who subsequently present with AST OR ALT values $>3 \times$ ULN AND a TBili value $>2 \times$ ULN with no evidence of hemolysis and an alkaline phosphatase value $<2 \times$ ULN or not available;
- For subjects with baseline AST **OR** ALT **OR** TBili values above the ULN, the following threshold values are used in the definition mentioned above, as needed, depending on which values are above the ULN at baseline:

- Preexisting AST or ALT baseline values above the normal range: AST or ALT values >2 times the baseline values AND $>3 \times$ ULN; or $>8 \times$ ULN (whichever is smaller).
- Preexisting values of TBili above the normal range: TBili level increased from baseline value by an amount of at least $1 \times$ ULN **or** if the value reaches $>3 \times$ ULN (whichever is smaller).

Rises in AST/ALT and TBili separated by more than a few weeks should be assessed individually based on clinical judgment; any case where uncertainty remains as to whether it represents a potential Hy's law case should be reviewed with the sponsor.

The subject should return to the investigator site and be evaluated as soon as possible, preferably within 48 hours from awareness of the abnormal results. This evaluation should include laboratory tests, detailed history, and physical assessment.

In addition to repeating measurements of AST and ALT and TBili, laboratory tests should include albumin, creatine kinase (CK), direct and indirect bilirubin, gamma-glutamyl transferase (GGT), prothrombin time (PT)/international normalized ratio (INR), total bile acids, alkaline phosphatase, and acetaminophen drug and/or protein adduct levels.

Consideration should also be given to drawing a separate tube of clotted blood and an anticoagulated tube of blood for further testing, as needed, for further contemporaneous analyses at the time of the recognized initial abnormalities to determine etiology. A detailed history, including relevant information, such as review of ethanol, acetaminophen (either by itself or as a coformulated product in prescription or over-the-counter medications), recreational drug, supplement (herbal) use and consumption, family history, sexual history, travel history, history of contact with a jaundiced person, surgery, blood transfusion, history of liver or allergic disease, and potential occupational exposure to chemicals, should be collected. Further testing for acute hepatitis A, B, C, D, and E infection and liver imaging (eg, biliary tract) may be warranted.

All cases demonstrated on repeat testing as meeting the laboratory criteria of AST/ALT and TBili elevation defined above should be considered potential DILI (Hy's law) cases if no other reason for the LFT abnormalities has yet been found. **Such potential DILI (Hy's law) cases are to be reported as SAEs, irrespective of availability of all the results of the investigations performed to determine etiology of the LFT abnormalities.**

A potential DILI (Hy's law) case becomes a confirmed case only after all results of reasonable investigations have been received and have excluded an alternative etiology.

8.4.3. Exposure to the Investigational Product during Pregnancy or Breastfeeding, and Occupational Exposure

Exposure to the investigational product under study during pregnancy or breastfeeding and occupational exposure are reportable to Pfizer Safety within 24 hours of investigator awareness.

8.4.3.1. Exposure during Pregnancy

For both unapproved/unlicensed products and for marketed products, an EDP occurs if:

- A female becomes, or is found to be, pregnant either while receiving or having been exposed (eg, because of treatment or environmental exposure) to the investigational product; or the female becomes or is found to be pregnant after discontinuing and/or being exposed to the investigational product;
 - An example of environmental exposure would be a case involving direct contact with a Pfizer product in a pregnant woman (eg, a nurse reports that she is pregnant and has been exposed to chemotherapeutic products).
- A male has been exposed (eg, because of treatment or environmental exposure) to the investigational product prior to or around the time of conception and/or is exposed during his partner's pregnancy.

If a subject or subject's partner becomes or is found to be pregnant during the subject's treatment with the investigational product, the investigator must report this information to Pfizer Safety on the CT SAE Report Form and an EDP supplemental form, regardless of whether an SAE has occurred. In addition, the investigator must submit information regarding environmental exposure to a Pfizer product in a pregnant woman (eg, a subject reports that she is pregnant and has been exposed to a cytotoxic product by inhalation or spillage) to Pfizer Safety using the EDP supplemental form. This must be done irrespective of whether an AE has occurred and within 24 hours of awareness of the exposure. The information submitted should include the anticipated date of delivery (see below for information related to termination of pregnancy).

Follow-up is conducted to obtain general information on the pregnancy and its outcome for all EDP reports with an unknown outcome. The investigator will follow the pregnancy until completion (or until pregnancy termination) and notify Pfizer Safety of the outcome as a follow-up to the initial EDP supplemental form. In the case of a live birth, the structural integrity of the neonate can be assessed at the time of birth. In the event of a termination, the reason(s) for termination should be specified and, if clinically possible, the structural integrity of the terminated fetus should be assessed by gross visual inspection (unless preprocedure test findings are conclusive for a congenital anomaly and the findings are reported).

If the outcome of the pregnancy meets the criteria for an SAE (ie, ectopic pregnancy, spontaneous abortion, intrauterine fetal demise, neonatal death, or congenital anomaly [in a live-born baby, a terminated fetus, an intrauterine fetal demise, or a neonatal death]), the investigator should follow the procedures for reporting SAEs.

Additional information about pregnancy outcomes that are reported to Pfizer Safety as SAEs follows:

- Spontaneous abortion includes miscarriage and missed abortion;
- Neonatal deaths that occur within 1 month of birth should be reported, without regard to causality, as SAEs. In addition, infant deaths after 1 month should be reported as SAEs when the investigator assesses the infant death as related or possibly related to exposure to the investigational product.

Additional information regarding the EDP may be requested by the sponsor. Further follow-up of birth outcomes will be handled on a case-by-case basis (eg, follow-up on preterm infants to identify developmental delays). In the case of paternal exposure, the investigator will provide the subject with the Pregnant Partner Release of Information Form to deliver to his partner. The investigator must document in the source documents that the subject was given the Pregnant Partner Release of Information Form to provide to his partner.

8.4.3.2. Exposure during Breastfeeding

Scenarios of exposure during breastfeeding must be reported, irrespective of the presence of an associated SAE, to Pfizer Safety within 24 hours of the investigator's awareness, using the CT SAE Report Form. An exposure during breastfeeding report is not created when a Pfizer drug specifically approved for use in breastfeeding women (eg, vitamins) is administered in accord with authorized use. However, if the infant experiences an SAE associated with such a drug's administration, the SAE is reported together with the exposure during breastfeeding.

8.4.3.3. Occupational Exposure

An occupational exposure occurs when, during the performance of job duties, a person (whether a healthcare professional or otherwise) gets in unplanned direct contact with the product, which may or may not lead to the occurrence of an AE.

An occupational exposure is reported to Pfizer Safety within 24 hours of the investigator's awareness, using the CT SAE Report Form, regardless of whether there is an associated SAE. Since the information does not pertain to a subject enrolled in the study, the information is not recorded on a CRF; however, a copy of the completed CT SAE Report Form is maintained in the investigator site file.

8.4.4. Medication Errors and Lack of Efficacy

Other exposures to the investigational product under study may occur in clinical trial settings, such as medication errors and lack of efficacy.

Safety Event	Recorded on the CRF	Reported on the CT SAE Report Form to Pfizer Safety Within 24 Hours of Awareness
Medication errors and lack of efficacy. ^a	All (regardless of whether associated with an AE)	Only if associated with an SAE

a. For lack of efficacy (particularly for studies conducted with vaccines, contraceptives, and products used in the treatment of life-threatening diseases or conditions [eg, anti-infectives]), see the Lack of Efficacy section below.

8.4.4.1. Medication Errors

Medication errors may result from the administration or consumption of the investigational product by the wrong subject, or at the wrong time, or at the wrong dosage strength.

Medication errors include:

- Medication errors involving subject exposure to the investigational product;
- Potential medication errors or uses outside of what is foreseen in the protocol that do or do not involve the participating subject;
- The administration of expired investigational product;
- The administration of an incorrect investigational product;
- The administration of an incorrect dosage;
- The administration of investigational product that has undergone temperature excursion from the specified storage range, unless it is determined by the sponsor that the investigational product under question is acceptable for use.

Such medication errors occurring to a study participant are to be captured on the medication error page of the CRF, which is a specific version of the AE page.

In the event of a medication dosing error, the sponsor should be notified immediately.

Whether or not the medication error is accompanied by an AE, as determined by the investigator, the medication error is recorded on the medication error page of the CRF and, if applicable, any associated AE(s), serious and nonserious, are recorded on an AE page of the CRF.

Medication errors should be reported to Pfizer Safety within 24 hours on a CT SAE Report Form **only when associated with an SAE**.

8.4.4.2. Lack of Efficacy

Lack of efficacy in an approved indication should be reported as an SAE to Pfizer Safety.

8.5. Medical Device Complaint Reporting Requirements

All medical device complaints, regardless of whether the medical device complaint is associated with an AE, will be recorded on the applicable pages within the CRF. This includes potential incidents or malfunctions associated with the use of a medical device product. An incident or malfunction is an event that might have led to death or serious deterioration in health, or if it occurred again might lead to death or serious deterioration in health.

Pfizer is to be notified of all medical device complaints within 24 hours of the investigator's awareness of the event.

9. DATA ANALYSIS/STATISTICAL METHODS

Detailed methodology for summary and statistical analyses of the data collected in this study is outlined here and further detailed in a statistical analysis plan (SAP), which will be maintained by the sponsor. The SAP may modify what is outlined in the protocol where appropriate; however, any major modifications of the primary endpoint definitions or their analyses will also be reflected in a protocol amendment.

9.1. Sample Size Determination

The study size is not based on any formal statistical hypothesis test. Approximately 220 adults per vaccine group are planned to be randomized. No formal statistical comparisons between vaccine groups are planned. Therefore, no power calculations for comparison of vaccine groups are included; however, the probabilities of at least 1 AE are calculated for range of assumed true event rates.

With approximately 200 subjects per vaccine group, the probabilities of observing at least 1 AE, local reaction, or systemic event where the true rate is 0.1%, 0.5%, 1%, and $\geq 5\%$ are 0.198, 0.668, 0.890, and >0.999 , respectively.

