3.3. Number of Subjects

Approximately 440 subjects (220 per group) will be randomized for a total of approximately 400 evaluable subjects (assuming a 10% dropout rate). Subjects who withdraw or are withdrawn from the study after randomization will not be replaced, regardless of the reason for withdrawal.

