9.2. Analysis Populations

The safety population will include all subjects who receive 1 dose of 20vPnC or 13vPnC. Subjects will be assigned to vaccine groups corresponding to the vaccine actually received. The safety population will be the only analysis population for the primary endpoints.

The evaluable immunogenicity population will generally include any subject:

1. who receives the assigned vaccine as randomized,
2. whose has either Visit 2 or Visit 3 blood collection within 27 to 49 days, inclusive, after vaccination, and

3. who has CCI OPA titers CCI for at least 1 serotype for either the Visit 2 time point (which is 1 month after Vaccination 1) or the Visit 3 time point (which is 1 month after Vaccination 2); however, at least 1 nonmissing value must be obtained 27 to 49 days, inclusive, after the indicated vaccination.

A subject may be included in the evaluable population even if one of the Visit 2 or Visit 3 blood collections is outside the window. However, titers CCI obtained outside the window will be excluded from the evaluable population analysis. Additional criteria (eg, without major protocol violations) are described in the SAP.

The evaluable immunogenicity population will be the primary analysis population for immunogenicity results.

The all-available immunogenicity population will include all subjects who receive 20vPnC or 13vPnC and have CCI 1 valid and determinate OPA titer CCI after either vaccination. The all-available immunogenicity population will be the secondary analysis population for immunogenicity results. Subjects will be assigned to their randomized vaccine.

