4. ANALYSIS SETS

4.1. Safety Analysis Population

The safety population will include all subjects who receive 1 dose of 20vPnC or 13vPnC. Subjects will be assigned to vaccine group corresponding to the vaccine actually received. Subjects who lack any safety data for an indicated analysis may be excluded from that analysis.

All safety analyses will be performed on an “as-received” basis and will not include data from subjects who are randomized but do not receive investigational product.

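### Protocol Section 9.1 labels its at-least-one-event probabilities as for about 200 subjects per group, but the printed values are those for 220

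*Protocol*

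**What the plan says.** Protocol Section 9.1 explains that the study size does not come from a hypothesis test and that no power calculation is given. It sets the group size: "Approximately 220 adults per vaccine group are planned to be randomized". It then offers detection probabilities instead: "With approximately 200 subjects per vaccine group, the probabilities of observing at least 1 AE, local reaction, or systemic event". Four assumed rates are listed, namely 0.1%, 0.5%, 1% and 5% or more, and the values given for them "are 0.198, 0.668, 0.890, and >0.999".

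The numbers 220 and 200 are different quantities in this protocol. Section 3.3 states: "Approximately 440 subjects (220 per group) will be randomized for a total of approximately 400 evaluable subjects", on an assumed dropout of 10%. Halving the evaluable total gives about 200 per group.

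On the population for these events, Protocol Section 9.2 says: "The safety population will be the only analysis population for the primary endpoints". SAP Section 4.1 defines it: "The safety population will include all subjects who receive 1 dose of 20vPnC or 13vPnC". The SAP neither repeats nor corrects the probabilities.

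**The concern.** Each printed probability follows from two inputs, the true rate and the number of subjects. The rate is given beside each value, so the number of subjects can be recovered and compared with the label. The two disagree.

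These probabilities are the only statement in the protocol of what the sample size can detect, and they concern the primary (safety) objective. A reader who takes the sentence at face value believes that 200 subjects per group, the number expected after dropout, give the stated chance of seeing an uncommon event. They give a smaller one.

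**Working it through.** **Inputs.** From Protocol Section 9.1: true rates p = 0.001, 0.005, 0.01 and 0.05; labelled n = 200 per group; printed probabilities 0.198, 0.668, 0.890 and >0.999. From Sections 3.3 and 9.1: 220 per group randomized.

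**Formula.** For n independent subjects with event probability p, the chance of at least one event is P = 1 − (1 − p)^n.

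**Step 1: evaluate at the labelled n and at the number randomized.**

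| True rate | Printed | n = 200 | Printed minus n = 200 | n = 220 |
|---|---|---|---|---|
| 0.1% | 0.198 | 0.18135 | 0.0166 | 0.19757 |
| 0.5% | 0.668 | 0.63304 | 0.0350 | 0.66805 |
| 1% | 0.890 | 0.86602 | 0.0240 | 0.89042 |
| 5% | >0.999 | 0.99996 | agrees | 0.99999 |

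At n = 220 every printed value is reproduced to three decimals. At n = 200 the first three are not. The last entry is satisfied by both and does not discriminate.

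**Step 2: solve for n.** Rearranging, n = ln(1 − P) / ln(1 − p). Allowing each printed value its rounding range of ±0.0005:

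- 0.198 at 0.1%: n between 219.9 and 221.2
- 0.668 at 0.5%: n between 219.7 and 220.3
- 0.890 at 1%: n between 219.2 and 220.1

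The only integer in all three ranges is 220. The neighbouring integers already fail: 219 gives 0.197, 0.666 and 0.889, and 221 gives 0.198, 0.670 and 0.892.

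**Step 3: look for another route to the printed values.**

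- The Poisson form 1 − exp(−np) at n = 200 gives 0.181, 0.632 and 0.865, which does not match.
- Applying 10% dropout exactly gives 440 × 0.9 = 396, or 198 per group. The values are then 0.180, 0.629 and 0.863, further from those printed.
- Pooling the groups does not fit either: at a 0.1% rate, 400 subjects give 0.330 and 440 give 0.356.

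**Step 4: restate the difference as the chance of missing an event.** At a true rate of 1%, the chance of seeing no event is 1 − 0.866 = 13.4% with 200 subjects, against the 1 − 0.890 = 11.0% that the printed value implies.

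**The case against.** The strongest reply is that this is a slip in a label and the probabilities themselves are right. They concern adverse events, local reactions and systemic events, all analysed in the safety population, which takes in everyone given dose 1. Under Protocol Section 6.1, randomization comes immediately before the Visit 1 blood draw and vaccination, so few subjects should be lost before dosing and the safety population should be close to 220 per group. The figure of 200 per group appears in Section 3.3 only as half of an evaluable total, and Sections 9.2 (Protocol) and 4.2 (SAP) use the word evaluable for the immunogenicity population. A reader who repeats the calculation can also recover 220.

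Most of this stands, and it makes the label the likelier error. It does not settle the matter. SAP Section 4.1 allows subjects without safety data to be left out of a given analysis, so the number contributing could fall below 220, and the label of 200 does agree with the after-dropout figure in Section 3.3.

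A second reply is that the text says approximately. That does not help: values printed to three decimals fix n at 220, and the same section uses approximately 220 for the number randomized.

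A third is that the study is descriptive. That is correct and limits the weight of the point, but it does not make the sentence right.

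**Conclusion.** The concern holds. The stated number of subjects and the stated probabilities in Protocol Section 9.1 are inconsistent, and 220 per group is the only number that produces the printed values. This assumes the usual binomial calculation with independent subjects and the rates as listed.

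The size depends on which number was meant. If 220, all four probabilities are correct and one number in the label is wrong. If 200, three of the four are overstated, by at most 3.5 percentage points. The documents do not say which, though the population for the primary endpoints favours 220.

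The point is minor. No enrolment number, test, decision rule, analysis population or confidence interval depends on these figures.

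**What to change.** State in Protocol Section 9.1 which number is intended and make the sentence agree with it. There are two ways:

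1. Change the label to approximately 220 vaccinated subjects per vaccine group and keep 0.198, 0.668, 0.890 and >0.999. This matches the safety population in Protocol Section 9.2 and SAP Section 4.1 and is the better supported choice.
2. Keep approximately 200, say that it is the number expected after 10% dropout, and print 0.181, 0.633, 0.866 and >0.999.

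The first changes one number and adds a word; the second changes three numbers and adds a short explanation. Either is confined to one protocol sentence and leaves enrolment, the analyses and the SAP as they are. Only the second makes the stated figures slightly less favourable.
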